## **7. STUDY EVALUATIONS**

### **7.1. Time and Event Schedule**

Table 4: Time and Events

Visit Information	PHASE 1 Visit 1 Screening, Baseline, Assessment Final Evaluation	PHASE 2 Visit 1 Screening, Baseline, Fitting / Assessment Final Evaluation
Time Point	Day 0	Day 0
Estimated Visit Duration	1.0 hours	3.0 hours
Statement of Informed Consent	X	X
Demographics	X	X
Medical History/Concomitant Medications	X	X
Habitual Contact Lens Information	X	X
Eligibility Following Screening	X	X
Entrance Visual Acuity	X	X
Subjective Sphero-Cylindrical Refraction and best-corrected VA		X
Eye Dominancy		X
Slit Lamp Biomicroscopy	X	X
Eligibility Following Baseline Evaluation	X	X
Lens Selection		X
Lens Insertion & Settling		X
Visual Acuity and Over Refraction		X
Lens Power Modification (if applicable)		X
Subject Reported Ocular Symptoms		X
Visual Acuity		X
General Fit Assessment		X

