**Clinical Study Protocol**  
**Johnson & Johnson Vision Care, Inc.**

Phase 2: Visit 1: Treatment 1 Lens Fitting		
Step	Procedure	Details
1.23	Lens Selection	
Assign the study lens based on the randomization scheme provided by the biostatistician.
 
Select the contact lens power [REDACTED] based on vertexed spherical equivalent from the refraction.

1.24	Lens Insertion	
The Investigator or the subject inserts the study lenses. Record the time of lens insertion.
 
Check for lens damage under the slit lamp before proceeding with lens settling.
 
Replace damaged lenses if applicable.
 
Ensure the subject is given a Patient Instruction Guide.

1.25	Lens Settling	Allow the study lenses to settle for a minimum of 5 minutes.
1.26	Subjective Best Sphere Over Refraction	Perform subjective best sphere refraction over the study lenses (adopt the maximum plus to maximum visual acuity (MPMVA) approach).
1.27	Lens Power Modification (if applicable)	
Adjust the lens power if the subject's best sphere over-refraction is not plano.
 
For each power modification, select the adjusted fitting lens power as appropriate and repeat steps 1.12 through 1.14.
 
Up to two power modifications are allowed per eye.

1.28	Subject Reported Ocular Symptoms	Subjects will respond to a verbal open-ended symptoms questionnaire.
1.29	Visual Acuity	Record the best corrected Snellen distance visual acuity to the nearest letter (OD and OS). Subjects must read the smallest line until at least 50% of the letters are read incorrectly. Visual acuity with the study contact lenses must be 20/30 or better OD and OS.

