**Clinical Study Protocol**  
**Johnson & Johnson Vision Care, Inc.**

Phase 2: Visit 1: Treatment 1 Lens Fitting		
Step	Procedure	Details
1.30	General Lens Fit Assessment	
Evaluate lens centration, movement on blink, and push-up test for each eye.
 
An unacceptable fit is deemed by one of the following criteria:
 
 
• limbal exposure at primary gaze or with extreme eye movement.
 
• edge lift.
 
• excessive movement in primary and up gaze.
 
• insufficient movement in all three of the following conditions: primary gaze, up gaze, and push-up test.
 
 
Note: if lens fit is unacceptable for either eye, the subject will be discontinued from the study.

1.31	Continuance	
For the subject to continue in the study, they must meet all three of the following criteria:
 
 
1. Visual acuity is 20/30 or better OD and OS.
 
2. The lens fit is acceptable OD and OS.
 
3. Investigator approval.
 
 
If the Investigator does not approve the study lens, then the study is terminated for that subject.

1.32	Lenses Worn in Clinic	
The lenses will be released for approximately two hours.
 
 
1. The subjects must wear both study lenses the entire time.
 
2. The lenses will be worn as daily wear only.
 
3. Rewetting drops are permitted if needed.
 
 
Note: In the event a lens is lost or damaged, it will be replaced immediately.
 
Note: A clinic-only-wear Patient Instruction Guide will be provided.

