**Clinical Study Protocol**  
**Johnson & Johnson Vision Care, Inc.**

1.34	
Visual Performance Testing With Glare
 
Visual performance testing will be performed using the Metropsis system OD and OS in the following order. The eye not being tested will be patched. The spectral output and intensity of the broadband light source will be verified before each test.
 
With glare OD:
 
 
1. Photopic resolution acuity           
 
A. Test distance: 4.0 m
 
B. Screen luminance approximately 120 cd/m^2
 
C. Ambient luminance must be dark with no lights or reflective surfaces within the general field of view of the target. EDC to record: Arcminute +/- SD. Range 0.2 - 60.0 arc minutes.
 
D. Rest a minimum of 2 minutes before next test
 
 
 
2. Photopic contrast sensitivity           
 
A. Test distance: 1.5 m
 
B. Screen luminance approximately 120 cd/m^2
 
C. Ambient luminance must be dark with no lights or reflective surfaces within the general field of view of the target.
 
D. Spatial frequencies 3, 6, 9, 12, 18 using a 2 degree Gabor stimulus. EDC to record: contrast threshold mean +/- SD for each spatial frequency. Range 0.0000 – 100.0000.
 
E. Rest a minimum of 5 minutes before next test
 
 
 
3. Mesopic contrast sensitivity           
 
A. Test distance: 1.5 m
 
B. Screen luminance approximately 3 cd/m^2
 
C. Add a 0.52 log unit ND filter to glare source
 
D. Ambient luminance must be dark with no lights or reflective surfaces within the general field of view of the target
 
E. Spatial frequencies 1.5, 3, 6, 9, 12 using a 2 degree Gabor stimulus. EDC to record: contrast threshold
 
 
 
 	------	--	--

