**FINAL EVALUATION**

The final evaluation will ordinarily take place immediately following the last scheduled procedure per the study protocol. It may also take place at any point the subject discontinues the study or is terminated from the study.

Final Evaluation		
Step	Procedure	Details
F.1	Final Exam Form	Indicate if the subject completed the study successfully. If subject discontinued from the study, indicate the reason.
F.2	Exit Slit Lamp Biomicroscopy	
FDA Slit Lamp Classification Scale will be used to grade the findings.
 
If the clearance of the fluorescein needs to be expedited, preservative-free rewetting drops or saline may be instilled. This step is not necessary if the subject was exited due to screen failure.

F.3	Exit Visual Acuity	Record the distance Snellen visual acuity (OD, OS, and OU) to the nearest letter with their habitual correction in place. Subjects must read the smallest line until at least 50% of the letters are read incorrectly.

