**Clinical Study Protocol**  
**Johnson & Johnson Vision Care, Inc.**

- Chief complaint prompting the visit. If the reason is an adverse event, the applicable eCRF for the adverse event must be completed and subject record completed as appropriate.
- Date and time of the visit and all procedures completed at the unscheduled visit.
- Review of adverse event and concomitant medications.
- Documentation of any test article dispensed or collected from the subject, if applicable.
- Slit lamp findings (using the Slit Lamp Classification Scale).

If the Investigator withdraws a subject from the study, the final study visit case report forms must be completed indicating the reason(s) why the subject was withdrawn. The subject record must be completed documenting the date and primary reason for withdrawal and the study CRA notified.

Any ocular and non-ocular Adverse Events that are ongoing at the time of the study visit will be followed by the Investigator, within licensure, until they have resolved, returned to pre-treatment status, stabilized, or been satisfactorily explained. If further treatment i.e., beyond licensure is required, the subject will be referred to the appropriate health care provider.

The following information will be collected during an unscheduled visit.

Unscheduled Visit		
Step	Procedure	Details
U.1	Reason for unscheduled visit	Indicate if the only reason for the visit is that the subject requires additional test articles. If the reason is other than resupply of previously dispensed lenses, specify the reason for the visit.
U.2	Chief Complaints (if applicable)	Record the subject's chief complaints for reasons for the unscheduled visit.
U.3	Adverse Events and Concomitant Medications Review (if applicable)	Review any changes to the subject's medical history or concomitant medications from the previous study visit. Record any changes, and any adverse events.
U.4	Entrance VA (if applicable)	Record the entrance distance visual acuity (OD, OS, and OU) to the nearest letter.
U.5	Subjective Sphero-cylindrical Refraction (if applicable)	Perform bare-eye subjective sphero-cylindrical refraction with a phoropter (adopt the maximum plus to maximum visual acuity (MPMVA) approach and use the duo-chrome test for binocular balancing) and record the best corrected distance visual acuity to the nearest letter (OD, OS, and OU).

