## **9. PRE-STUDY AND CONCOMITANT INTERVENTION/MEDICATION**

Concomitant medications will be documented during screening and updated during the study. Disallowed medications for this study include: any ocular medications. Concomitant therapies that are disallowed include: see section 9.1.

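### The only scheduled symptom question comes before the two-hour wear and the glare testing, and no later scheduled step in either phase asks about symptoms, adverse events or medication changes

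*Combined protocol and SAP*

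**What the plan says.** Phase 2 is a single visit. In section 7.2 the lenses go in at step 1.24, and step 1.25 says "Allow the study lenses to settle for a minimum of 5 minutes". Over-refraction and any power change follow. Step 1.28 then says "Subjects will respond to a verbal open-ended symptoms questionnaire". After acuity, fit assessment and the decision to continue, step 1.32 says "The lenses will be released for approximately two hours". Step 1.33 is the testing without glare, step 1.34 is "Visual Performance Testing With Glare" in each eye, and step 1.35 is lens removal.

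The Final Evaluation, used in both phases, has three items. F.1 is a form: "Indicate if the subject completed the study successfully. If subject discontinued from the study, indicate the reason". F.2 is exit slit lamp biomicroscopy and F.3 is exit visual acuity.

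Table 4 in section 7.1 has one row named "Subject Reported Ocular Symptoms". It is marked for Phase 2 only and sits above the vision assessments. The table has no adverse event row. Section 9 states: "Concomitant medications will be documented during screening and updated during the study". Within section 7, a review of adverse events and medications appears only under unscheduled visits (section 7.3, step U.3).

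Section 13.3 starts adverse event recording at exposure to the test article, study treatment or study procedure. It requires every event during enrollment to be documented, whatever its relationship to treatment.

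**The concern.** The study exposes subjects to an investigational lens for a few hours (Phase 2) and to a broadband glare source (both phases). The one scheduled question about how the eyes feel is put before most of the wear and before any glare. A site that follows the numbered steps has no prompt to ask again.

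Transient discomfort, after-images or light sensitivity can occur without a slit lamp finding or a loss of acuity. With no prompt, such complaints reach the record only when a subject raises them, and volunteered reports tend to be fewer and less uniform than solicited ones. The definitions in section 13.1 also depend partly on symptoms: significant events are described as symptomatic, non-significant ones as usually asymptomatic. Under section 13.4 that class sets the reporting time (24 hours or 2 days).

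At stake is the completeness of adverse event ascertainment. The efficacy result is not at stake.

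**Working it through.** No arithmetic lies behind this point beyond counting. The check is to list the scheduled steps in order and note what each one asks the subject.

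| Step (section 7.2) | Content | Timing | Asks about symptoms, events or medication? |
|---|---|---|---|
| 1.15 (Phase 2), 1.3 (Phase 1) | Medical history, medications | Screening | Yes, baseline only |
| 1.25 | Settling, 5 minutes or more | Start of lens exposure | No |
| 1.28 | Verbal symptom question | Before 1.32 and 1.34 | Yes, symptoms |
| 1.32 | In-clinic wear, about two hours | Exposure | No |
| 1.33 | Testing without glare | Exposure | No |
| 1.34 (Phase 2), 1.12 (Phase 1) | Testing with glare | Exposure | No |
| 1.35 | Lens removal (Phase 2) | After | No |
| F.1 | Completion form | After | No, except the reason if the subject discontinued |
| F.2 | Exit slit lamp | After | No, objective signs |
| F.3 | Exit acuity | After | No, measured function |

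Counts from this list:

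- Phase 2: scheduled symptom questions, 1 (step 1.28). Scheduled questions on symptoms or adverse events after step 1.28, 0. Objective checks after exposure, 2 (F.2 and F.3).
- Phase 1: scheduled symptom questions, 0. Scheduled questions on symptoms or adverse events after glare, 0. Objective checks after exposure, 2.
- Subjects concerned: up to 66 in Phase 2 plus up to 24 in Phase 1, so 66 + 24 = 90 (section 4.3).

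Table 4 agrees with the step list. Section 4.3 gives one visit per subject in each phase, so no later scheduled contact could supply the question.

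The protocol does not say whether the testing falls inside or after the two hours of step 1.32. The finding is the same either way, because step 1.28 precedes both. Step 1.28 does follow a short lens exposure, so initial insertion is covered by a symptom question; the longer wear and the glare are not.

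Sections 9 and 7 do not match on medications. Section 9 says they are updated during the study, but the only step that does this is U.3, which a subject without an unscheduled visit never reaches.

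**The case against.** The strongest reply is that safety after exposure is covered. The Final Evaluation follows the last procedure and includes a slit lamp examination and acuity in both phases. Section 13.3 requires documentation of every event, and section 13.4 sets the reporting times. A subject who stops because of symptoms would have that reason recorded at F.1. Exposure lasts only hours, in a clinic, in habitual lens wearers. All of this stands, and it limits the point to one of elicitation. It does not remove it: a duty to document what is found is not a step that asks.

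Appendix J, section 6.0, says participants are interviewed for safety data at each contact. Its setting is pandemic disruption, and it creates no step, row or form in this visit, so it helps only partly.

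Some material cannot be seen. The symptom procedure in Appendix D is redacted, and Figure 1 and the Metropsis Work Aid in Appendix H are not shown. Any of them could carry a prompt, so the finding is confined to the visible procedures.

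A reader might infer four stronger things that the documents do not support:

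- **That nothing checks safety after exposure.** F.2, F.3 and section 13.3 contradict this.
- **That the glare source is hazardous.** Section 1 reports that it was calculated safe under ANSI Z136.1-2014 for up to 350 minutes of photopic contrast testing and up to 150 minutes of acuity testing in a day. The target is only about a 0.1 log unit loss of contrast sensitivity, and a 0.52 log unit filter is added for mesopic testing.
- **That a planned Test-versus-Control symptom comparison is lost.** Sections 2.1 to 2.3 and 14 plan none, and Appendix A lists no patient-reported outcomes. Section 14.1 asks for summaries of safety variables as appropriate, which exit findings and recorded events can meet.
- **That Table 4 omits the exit slit lamp.** Its slit lamp row is marked in single-visit columns whose headings include the final evaluation, and F.2 governs in any case.

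**Conclusion.** The point holds as a gap in scheduled elicitation. In the visible procedures, Phase 2 asks about ocular symptoms once, before the main wear and the glare, and Phase 1 never asks. After exposure, none of the up to 90 subjects meets a scheduled question on symptoms, adverse events or medication changes. Symptoms without a slit lamp or acuity sign therefore depend on being volunteered, and the medication update in section 9 has no scheduled step behind it.

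How many symptoms would be missed cannot be estimated from the documents. No endpoint, error rate, power figure or analysis population is affected. This is a cheap improvement to adverse event ascertainment, not a flaw in the trial's inference. The conclusion assumes that the redacted and unshown material holds no further prompt; if it does, the remaining work is to align section 7.2 and Table 4 with it.

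**What to change.** Four edits, all reusing existing instruments:

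- **Phase 2:** repeat the verbal question of step 1.28 after step 1.34 and before lens removal at 1.35. Record it by eye, since the two eyes wear different lenses and section 13.2.1 asks for a relationship to the test article. Placed after the last measurement, it cannot disturb the psychophysical testing.
- **Phase 1:** ask the same question after step 1.12.
- **Final Evaluation:** add a review of adverse events and concomitant medications at F.1, which also gives section 9 a scheduled step.
- **Table 4:** add rows for the post-test symptom question and for the adverse event and medication review.

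The cost is one repeated eCRF page, edits to sections 7.1 and 7.2, and an estimated one to two minutes per subject (an assumption; the documents give no figure). Over 90 subjects that is 90 × 1 = 90 to 90 × 2 = 180 minutes in total. No new staff or equipment is needed. The change has to be in place before enrollment, because each subject has one visit and symptoms immediately after exposure cannot be collected reliably later.

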**Clinical Study Protocol**  
**Johnson & Johnson Vision Care, Inc.**

Phase 2: Visit 1: Treatment 1 Lens Fitting		
Step	Procedure	Details
1.30	General Lens Fit Assessment	
Evaluate lens centration, movement on blink, and push-up test for each eye.
 
An unacceptable fit is deemed by one of the following criteria:
 
 
• limbal exposure at primary gaze or with extreme eye movement.
 
• edge lift.
 
• excessive movement in primary and up gaze.
 
• insufficient movement in all three of the following conditions: primary gaze, up gaze, and push-up test.
 
 
Note: if lens fit is unacceptable for either eye, the subject will be discontinued from the study.

1.31	Continuance	
For the subject to continue in the study, they must meet all three of the following criteria:
 
 
1. Visual acuity is 20/30 or better OD and OS.
 
2. The lens fit is acceptable OD and OS.
 
3. Investigator approval.
 
 
If the Investigator does not approve the study lens, then the study is terminated for that subject.

1.32	Lenses Worn in Clinic	
The lenses will be released for approximately two hours.
 
 
1. The subjects must wear both study lenses the entire time.
 
2. The lenses will be worn as daily wear only.
 
3. Rewetting drops are permitted if needed.
 
 
Note: In the event a lens is lost or damaged, it will be replaced immediately.
 
Note: A clinic-only-wear Patient Instruction Guide will be provided.

**Clinical Study Protocol**  
**Johnson & Johnson Vision Care, Inc.**

1.33	
Visual Performance Testing Without Glare
	
Visual performance testing will be performed using the Metropsis system OD and OS in the following order. The eye not being tested will be patched.
 
Without glare OD:
 
 
1. Photopic resolution acuity           
 
A. Test distance: 4.0 m
 
B. Screen luminance approximately 120 cd/m^2
 
C. Ambient luminance must be dark with no lights or reflective surfaces within the general field of view of the target. EDC to record: Arcminute +/- SD. Range 0.2 - 60.0 arc minutes.
 
D. Rest a minimum of 2 minutes before next test
 
 
 
2. Photopic contrast sensitivity           
 
A. Test distance: 1.5 m
 
B. Screen luminance approximately 120 cd/m^2
 
C. Ambient luminance must be dark with no lights or reflective surfaces within the general field of view of the target
 
D. Spatial frequencies 3, 6, 9, 12, 18 using a 2 degree Gabor stimulus. EDC to record: contrast threshold mean +/- SD for each spatial frequency. Range 0.0000 – 100.0000.
 
E. Rest a minimum of 5 minutes before next test
 
 
 
3. Mesopic contrast sensitivity           
 
A. Test distance: 1.5 m
 
B. Screen luminance approximately 3 cd/m^2. This will be achieved by placing neutral density films over the Metropsis monitor.
 
C. Ambient luminance must be dark with no lights or reflective surfaces within the general field of view of the target
 
D. Spatial frequencies 1.5, 3, 6, 9, 12 using a 2 degree Gabor stimulus. EDC to record: contrast threshold mean +/- SD for each spatial frequency. Range 0.0000 – 100.0000.
 
 
 
	
------	---	---	--

**Clinical Study Protocol**  
**Johnson & Johnson Vision Care, Inc.**

Phase 2: Visit 1: Treatment 1 Lens Fitting		
Step	Procedure	Details
		
E. Rest a minimum of 2 minutes before next test
 
Without glare OS: Steps 1-3 listed above will be repeated for the alternate eye.

**Clinical Study Protocol**  
**Johnson & Johnson Vision Care, Inc.**

1.34	
Visual Performance Testing With Glare
 
Visual performance testing will be performed using the Metropsis system OD and OS in the following order. The eye not being tested will be patched. The spectral output and intensity of the broadband light source will be verified before each test.
 
With glare OD:
 
 
1. Photopic resolution acuity           
 
A. Test distance: 4.0 m
 
B. Screen luminance approximately 120 cd/m^2
 
C. Ambient luminance must be dark with no lights or reflective surfaces within the general field of view of the target. EDC to record: Arcminute +/- SD. Range 0.2 - 60.0 arc minutes.
 
D. Rest a minimum of 2 minutes before next test
 
 
 
2. Photopic contrast sensitivity           
 
A. Test distance: 1.5 m
 
B. Screen luminance approximately 120 cd/m^2
 
C. Ambient luminance must be dark with no lights or reflective surfaces within the general field of view of the target.
 
D. Spatial frequencies 3, 6, 9, 12, 18 using a 2 degree Gabor stimulus. EDC to record: contrast threshold mean +/- SD for each spatial frequency. Range 0.0000 – 100.0000.
 
E. Rest a minimum of 5 minutes before next test
 
 
 
3. Mesopic contrast sensitivity           
 
A. Test distance: 1.5 m
 
B. Screen luminance approximately 3 cd/m^2
 
C. Add a 0.52 log unit ND filter to glare source
 
D. Ambient luminance must be dark with no lights or reflective surfaces within the general field of view of the target
 
E. Spatial frequencies 1.5, 3, 6, 9, 12 using a 2 degree Gabor stimulus. EDC to record: contrast threshold
 
 
 
 	------	--	--

**Clinical Study Protocol**  
**Johnson & Johnson Vision Care, Inc.**

Phase 2: Visit 1: Treatment 1 Lens Fitting		
Step	Procedure	Details
		
mean +/- SD for each spatial frequency. Range 0.0000 – 100.0000.
 
F. Rest a minimum of 2 minutes before next test
 
With glare OS:            Steps 1-3 listed above will be repeated for the alternate eye.

1.35	Lens Removal	The worn study lenses will be removed and discarded.

**FINAL EVALUATION**

The final evaluation will ordinarily take place immediately following the last scheduled procedure per the study protocol. It may also take place at any point the subject discontinues the study or is terminated from the study.

Final Evaluation		
Step	Procedure	Details
F.1	Final Exam Form	Indicate if the subject completed the study successfully. If subject discontinued from the study, indicate the reason.
F.2	Exit Slit Lamp Biomicroscopy	
FDA Slit Lamp Classification Scale will be used to grade the findings.
 
If the clearance of the fluorescein needs to be expedited, preservative-free rewetting drops or saline may be instilled. This step is not necessary if the subject was exited due to screen failure.

F.3	Exit Visual Acuity	Record the distance Snellen visual acuity (OD, OS, and OU) to the nearest letter with their habitual correction in place. Subjects must read the smallest line until at least 50% of the letters are read incorrectly.

